### **5.8.6. Pediatric Outcomes Data Collection Instrument (PODCI)**

The two PODCI domains (transfers/mobility and sports participation) each provide a numerical score from 0-100. The PODCI domain scores and changes from baseline will be summarized by visit for ambulatory subjects.

### **5.8.7. Spirometry**

Pulmonary function parameters of %-predicated FVC, %-predicted FEV1 (adjusted using ulna length and age), peak expiratory flow (PEF), and peak cough flow (PCF) and their absolute and relative changes from baseline will be summarized by visit. Similarly the observed values of the endpoints will also be summarized for each actual age.

### **5.8.8. Performance Upper Limb (PUL) Assessment**

The PUL assessment includes 22 items (with an entry item to define starting functional level to avoid testing functional dimensions in which the subject lacks the lower limit of function, and 21 items subdivided into shoulder level (4 items), elbow level (9 items), and distal level (8 items) dimensions. Scoring varies across the scale from 0-1 to 0-6 according to performance. Each dimension will be scored separately with a maximum score of 16 for shoulder level, 34 for elbow level, and 24 for distal level. The total score will be calculated by adding the 3 level scores (maximum global score of 74). The total score and 3 dimension scores and their changes from baseline will be summarized by visit for non-ambulatory subjects. Similarly the PUL assessment will also be summarized for each actual age.

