3.3. Clinical Endpoints

Primary

- Safety profile characterized by type, frequency, severity, timing, and relationship to ataluren of any adverse events or laboratory abnormalities

Secondary

Physical

- Change in ambulation as measured by the 6MWT
- Change in proximal muscle function as assessed by timed function tests (time to rise from supine position, time to run 10 meters, and time to climb/descend 4 stairs)
- Change in physical function as assessed by the North Star Ambulatory Assessment

- Change in motor performance of the upper limb as measured by the Performance Upper Limb (PUL)

Pulmonary function

Change in pulmonary function as measured by spirometry (eg. FVC, FEV1)

Patient-Reported Outcomes

- Change in patient- and parent/caregiver-reported HRQL as measured by the PODCI Transfer/Basic Mobility and Sports/Physical Functioning scores
- Change in patient and parent/caregiver reported activities of daily living

Exposure

- Pre-dose ataluren plasma concentrations prior to morning ataluren administration at each clinic visit as assessed by a validated bioanalytical method

Safety

- Change from baseline in other safety parameters (eg, vital signs)

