7.18. Performance of Upper Limb Assessment (PUL)

The PUL assessment will be performed to evaluate upper limb function. The PUL assessment will be performed at Screening/Baseline on Visit 1, Week 12 (Visit 2), Week 24 (Visit 3), Week 36 (Visit 4), Week 48 (Visit 5), Week 60 (Visit 6), Week 72 (Visit 7), Week 84 (Visit 8), and Week 96 (Visit 9) Week 108 (Visit 10), Week 120 (Visit 11), Week 132 (Visit 12), Week 144 (Visit 13- End-of-Treatment/Premature Discontinuation).

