10.5.5. Performance Upper Limb (PUL) Assessment

The PUL assessment includes 22 items (with an entry item to define starting functional level to avoid testing functional dimensions in which the patient lacks the lower limit of function, and 21 items subdivided into shoulder level (4 items), elbow level (9 items), and distal level (8 items) dimensions. Scoring varies across the scale between 0-1 to 0-6 according to performance. Each dimension will be scored separately with a maximum score of 16 for shoulder level, 34 for elbow level, and 24 for distal level. Total score will be calculated by adding the 3 level scores (maximum global score of 74). Changes from baseline will be described by patient and visit and summarized by visit and overall.

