##### *Physical*

- To determine the effect of ataluren on ambulation in patients who are ambulatory.
- To evaluate the effect of ataluren on proximal muscle function in patients who are able to perform timed function tests.
- To evaluate the effect of ataluren on physical function in patients who are able to perform the North Star Ambulatory Assessment.
- To evaluate the effect of ataluren on upper limb function.

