## **5. STATISTICAL ANALYSIS**

### **5.1. General Statistical Considerations**

Summary tables for continuous variables will contain the following statistics: n, mean, standard deviation, standard error, 95% confidence intervals (CIs) on the mean, median, minimum, and maximum. Summary tables for categorical variables will include N, n, and percentages. In by-visit summaries, the analysis visits will be derived via visit mapping windows.

For descriptive summary tables, the all data will be analyzed and displayed by ambulatory status (ambulatory or non-ambulatory) at baseline, unless specified otherwise. Where applicable, the summary data (mean, standard error) will be presented in graphical form of against time of visit.

By-patient listings will be created for each CRF module. The data will be listed by center/subject ID and visit.

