## 5.3. Demographic and Baseline Characteristics

Subject demographic and disease characteristics (age, age group (6-11, 12-17, and  $\geq 18$  years), gender, race, ethnicity, height, weight, body mass index, six minute walk distance, six minute walk distance groups ( $<300$  meters,  $\geq 300$ - $<400$  meters,  $\geq 400$  meters), time to run/walk 10 meter, time to stand from supine, time to stand from supine ( $<5s$ ,  $\geq 5s$ ), performance of Upper Limb Assessment (PUL), corticosteroid use (Yes/No), and ambulatory/non-ambulatory) at study entry will be summarized for overall subjects, a subgroup of subjects with corticosteroid use duration ( $<12$  months,  $\geq 12$  months) at baseline, a subgroup of subjects with corticosteroid type (deflazacort vs prednisone/prednisolone) at baseline, and a subgroup of ambulatory/non-ambulatory subjects at study entry.

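### SAP 5.8.8 limits the by-visit PUL change summary to non-ambulatory boys, although the upper-limb objective and data collection cover all boys and SAP section 7 does not declare the change

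*SAP*

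**What the plan says.** SAP 3.2 repeats the protocol's secondary objective: "To evaluate the effect of ataluren on upper limb function". The three neighbouring physical objectives are confined to boys who are ambulatory or can perform the test concerned; this one is not. The matching endpoint (protocol 3.3, SAP 3.3) is change in PUL, with no subgroup.

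Protocol 7.18 gives the purpose of the test without any condition on walking: "The PUL assessment will be performed to evaluate upper limb function". Protocol Table 3 and SAP Table 1 schedule it at Visits 1 to 13 (baseline to Week 144) and not at Visit 14, the post-treatment visit.

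On analysis, protocol 10.5.5 says: "Changes from baseline will be described by patient and visit and summarized by visit and overall". SAP 5.8.8 says instead: "The total score and 3 dimension scores and their changes from baseline will be summarized by visit for non-ambulatory subjects". It then adds: "Similarly the PUL assessment will also be summarized for each actual age". The general rule in SAP 5.1 is that data are "displayed by ambulatory status (ambulatory or non-ambulatory) at baseline, unless specified otherwise". SAP section 1 gives the SAP precedence over the protocol.

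**The concern.** A secondary endpoint defined for all boys is to be summarised over time in only one group of them. The SAP gives no reason, and section 7, the place for departures from the protocol, does not mention it. The protocol's own rationale (13.4.4) presents the scale as built to reflect decline in ambulant as well as non-ambulant disease, so nothing in the documents suggests that scores from walking boys are uninformative.

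What is at stake is descriptive. Boys do the test up to 13 times over 144 weeks, yet for those classed as ambulatory the plan promises no clear account of how their scores change. Depending on how status is timed, that group may include boys who lose ambulation during the study.

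**Working it through.** There is no planned figure to reproduce: the extension has no formal hypothesis or power calculation, and about 220 is only an upper bound on its size (protocol 10.1, SAP 3.4). The check is a comparison of texts, followed by simple arithmetic on assumed shares.

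**Which planned outputs could show PUL change in ambulatory boys?**

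| Output | Source | Covers ambulatory boys? | Gives change from baseline? |
|---|---|---|---|
| By-visit scores and changes | SAP 5.8.8, first summary | No | Yes |
| By-age summary | SAP 5.8.8, last sentence | Not stated | Not stated |
| PUL at study entry | SAP 5.3 | Yes, overall and by status | No, entry only |
| By-patient listings | SAP 5.1 | Yes | Not a summary |
| Natural-history comparison | SAP section 8 | PUL is not among the endpoints | No |

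No row clearly combines ambulatory boys with change from baseline.

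**Is the narrowing declared?** SAP section 7 lists two changes: the 6MWT supportive analyses are dropped and all paired t-tests are dropped. The PUL restriction is neither.

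**When is ambulatory status assessed?** SAP 5.8.8 is silent. The 5.1 display rule uses status at baseline, while SAP 8.2 uses status at study entry for some analyses and at each assessment for another. SAP 5.8.4 analyses age at loss of ambulation, so such losses are expected.
- Status at baseline: a boy who stops walking during the study never enters the by-visit PUL summary.
- Status at assessment: he enters once he has stopped walking, and the set of boys summarised changes from visit to visit.

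**How many boys are left out?** With N = 220 (upper bound) and p the non-ambulatory share (assumed; in neither document), the number included is 220 × p and the number omitted is 220 × (1 − p). For scale, the approximate half-width of a 95% CI on a mean change, in SD units, is 1.96/√n.

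| Assumed p | Included | Omitted | Half-width |
|---|---|---|---|
| 5% | 11 | 209 (95%) | 1.96/√11 = 0.59 SD |
| 20% | 44 | 176 (80%) | 1.96/√44 = 0.30 SD |
| 50% | 110 | 110 (50%) | 1.96/√110 = 0.19 SD |
| All 220 summarised | 220 | 0 | 1.96/√220 = 0.13 SD |

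The half-widths indicate scale only. The mean over all boys and the mean over non-ambulatory boys are different quantities and may have different SDs, and fewer boys will contribute at later visits. More than half the cohort is omitted only if p is below 50%.

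**The case against.** The strongest defence is that the SAP follows a visible pattern. By-visit summaries of 6MWT, timed function tests, NSAA and PODCI are for ambulatory subjects (SAP 5.8.3 to 5.8.6), and PUL is for non-ambulatory subjects. The study is open-label, has no formal hypothesis and was stopped early, and efficacy analyses were trimmed as a result. No inferential or safety conclusion depends on this table. All of that stands, and it limits the weight of the point. It does not explain why a change to a protocol-stated summary is missing from section 7, or why a test given to every boy should go without a change summary for some of them.

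Three stronger readings are tempting and not supported.
- A reader might infer that the upper-limb objective goes unanswered for walking boys. The by-age summary may include them, their entry scores are tabulated and their data are listed. The gap is narrower: a clear summary of change.
- A reader might infer that most of the cohort is dropped. The restriction of several summaries to ambulatory boys and the grouping of baseline walking distance make an ambulatory majority plausible. Neither document gives the split, however, and the SAP plans non-ambulatory subgroups at entry.
- A reader might infer that boys who stop walking during the study are certainly excluded. That follows only if status is taken at baseline.

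A ceiling effect in stronger boys might be the unstated motive. The documents do not say so, and a ceiling can be shown rather than assumed.

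**Conclusion.** The point holds as an undeclared narrowing of a descriptive secondary summary. It follows from the texts alone and needs no assumption about cohort composition. Its size does need one: of at most about 220 boys, between 110 and 209 would be left out of the by-visit PUL summary for non-ambulatory shares between 50% and 5%. A share above 50% would leave out fewer. Whether boys who lose ambulation during the study are among them depends on a definition that SAP 5.8.8 does not give. No primary or safety result is affected; this is a free improvement, not a flaw that threatens the study's conclusions.

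**What to change.** In SAP 5.8.8:
- Delete the restriction to non-ambulatory subjects. Summarise PUL total and dimension scores and their changes by visit for all as-treated subjects, which restores protocol 10.5.5.
- Add columns by baseline ambulatory status. This is the SAP 5.1 default; the protocol does not itself ask for the split.
- State that the by-age summary covers all subjects.
- Report the percentage of boys at the maximum score (74 for the total; 16, 34 and 24 for shoulder, elbow and distal levels), so that any ceiling is visible.

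Boys who stop walking during the study will then appear in the baseline-ambulatory column; the table should say that status is fixed at baseline. If the restriction is kept instead, SAP 5.8.8 should say when status is assessed, and section 7 should declare and justify the change.

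The cost is table programming only. The data are already part of the visit schedule, and no further assessment is needed.

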### **5.8.9. Activities of Daily Living/Disease Status Survey**

For change in activities of daily living/disease status of prospective survey data, number (%) of subjects with changes from baseline to each visit will be summarized by each category for overall subjects. If there are multiple symptoms under a category, the highest score/worse case of all available symptoms was selected for the category in the summary.

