7.19. Activities of Daily Living/Disease Symptom Survey

A survey will be administered at Screening/Baseline on Visit 1, Week 12 (Visit 2), Week 24 (Visit 3), Week 36 (Visit 4), Week 48 (Visit 5), Week 60 (Visit 6), Week 72 (Visit 7), Week 84 (Visit 8), and Week 96 (Visit 9) Week 108 (Visit 10), Week 120 (Visit 11), Week 132 (Visit 12), Week 144 (Visit 13- End-of-Treatment/Premature Discontinuation) to collect prospective information on patient and/or parent-reported changes in activities of daily living and disease symptoms. The survey will be available in all languages relevant for this study and will be administered by the site staff to the parent/caregiver and/or patient.

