10.5.6. Activities of Daily Living/Disease Status Survey

Disease status survey data will be listed by patient and visit. Changes from baseline to each scheduled visit and to the final visit will be summarized descriptively.

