13.4.7. Activities of Daily Living and Disease Symptom Survey

There has been growing interest in seeking direct patient reporting of changes in symptoms and functioning during a clinical study [FDA 2009]. Such information may help to confirm more objective measures of patient benefit, and document how drug activity translates to improved well-being outside of the clinic. Anecdotal reports from parents and teachers of boys participating in prior studies of ataluren in nmDMD suggested that boys have experienced psychological, social and behavioral benefits (eg, less frustration with physical tasks, improved ability to play with other children) in association with improved endurance and reduced fatigue while receiving ataluren. To formally capture such reports, a disease symptom survey will be utilized to capture individualized patient and parent/caregiver-reported changes in activities of daily living and disease symptoms that are specific to dystrophinopathy and are not assessed in standardized questionnaires. This survey has been developed by PTC Therapeutics based upon reports from participants in previous ataluren studies. The survey will be available in all languages relevant for this study and will be administered by the site staff to the parent/caregiver and/or patient.

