## 1. OVERVIEW

This statistical analysis plan (SAP) details the statistical methods to be used in the analyses and presentation of the data collected in Study PTC124-GD-020e-DMD, also referred to as Study 020e. Preparation of this SAP incorporates statistical design elements present in the protocol amendment version 2.0 (dated 18 November 2015). Details are documented in sections 1-7.

In addition to the protocol defined analyses, a natural history control using the Cooperative International Neuromuscular Research Group (CINRG) will be utilized in order to help to better understand the long-term ataluren data. Although the planned analysis will not be included in the CSR it will be presented in Section 8 for completeness.

Where conflicts exist between this SAP and the study protocols, the information contained in this SAP supersedes the protocol.

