#### **Patient-Reported Outcomes**

- Change in patient- and parent/caregiver-reported HRQL as measured by the PODCI Transfer/Basic Mobility and Sports/Physical Functioning scores
- Change in patient and parent/caregiver reported activities of daily living

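### The only planned table of the activities-of-daily-living survey shows each multi-symptom category by its worst symptom; if the scores are change ratings, this leans towards worsening, and the SAP does not say what the score is.

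*SAP*

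**What the plan says.** The SAP lists this among its secondary endpoints, under Patient-Reported Outcomes: "Change in patient and parent/caregiver reported activities of daily living". Protocol 7.19 says the survey collects "patient and/or parent-reported changes in activities of daily living" and disease symptoms, and schedules it at Screening/Baseline as well as at the treatment visits. Protocol 13.4.7 gives its purpose: "Such information may help to confirm more objective measures of patient benefit".

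For the analysis, Protocol 10.5.6 asks for listings and says: "Changes from baseline to each scheduled visit and to the final visit will be summarized descriptively". SAP 5.8.9 is more specific: "number (%) of subjects with changes from baseline to each visit will be summarized by each category for overall subjects". It then adds the aggregation rule: "If there are multiple symptoms under a category, the highest score/worse case of all available symptoms was selected for the category in the summary".

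The SAP does not define the score, list the categories, give the number of symptoms in each, or say why the worst symptom was chosen. Symptom-level data otherwise appear only in the by-patient listings of SAP 5.1.

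**The concern.** The endpoint is change, which can go either way, and the survey was included partly so that benefit could be seen. Taking the worst of several items is natural in a safety display, where the aim is not to miss harm. For a two-directional endpoint it is lopsided if the items are change ratings: one worsened symptom settles the category, whereas improvement needs unanimity. As this is the only summary table for the endpoint, a reader of the study report could see a picture of deterioration produced partly by the rule, and could not recover the symptom-level picture except from listings.

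**Working it through.** The plan states no figure for this survey, so there is nothing to reproduce. The check is what the rule does under each reading of the word score.

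**Inputs.** From the documents: the worst-symptom rule and the tabulated quantity (SAP 5.8.9), and the fact that the survey records reported changes (Protocol 7.19). Assumed, because the documents do not give them: the number of symptoms per category (k), the share of boys with each symptom better (pB) or worse (pW), and the correlation between symptoms.

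**Reading A: each symptom carries a change rating, and the worst is taken.** Code better as −1, same as 0 and worse as +1; the category takes the maximum.

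- One better, one worse: max(−1, +1) = +1, worse.
- Four better, one worse: max(−1, −1, −1, −1, +1) = +1, worse.
- Three better, one unchanged: max(−1, −1, −1, 0) = 0, unchanged.

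Across boys, with independent symptoms, P(category worse) = 1 − (1 − pW)^k and P(category better) = pB^k. With correlated symptoms, each rating was obtained by cutting a normal variable with a common correlation at the points that give pB and pW, and the same two probabilities were found by numerical integration.

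*No net change: 20% better, 60% same, 20% worse per symptom.* For k = 3 and independence, 1 − 0.8³ = 48.8% and 0.2³ = 0.8%.

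| Symptoms | Correlation | Worse | Better |
|---|---|---|---|
| 1 | – | 20.0% | 20.0% |
| 2 | 0 | 36.0% | 4.0% |
| 3 | 0 | 48.8% | 0.8% |
| 3 | 0.5 | 38.9% | 5.0% |
| 3 | 0.9 | 27.8% | 12.8% |
| 5 | 0 | 67.2% | 0.03% |
| 5 | 0.5 | 48.8% | 2.4% |
| any | 1 | 20.0% | 20.0% |

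*Real benefit: 30% better, 60% same, 10% worse per symptom, a net 20 points towards better.* For k = 3 and independence, 1 − 0.9³ = 27.1% and 0.3³ = 2.7%.

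| Symptoms | Correlation | Worse | Better |
|---|---|---|---|
| 3 | 0 | 27.1% | 2.7% |
| 3 | 0.5 | 21.8% | 10.1% |
| 3 | 0.7 | 19.0% | 14.4% |
| 3 | 0.9 | 15.0% | 20.9% |

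The direction is reversed up to correlation 0.7. At 0.9 it is kept, but the net benefit shrinks from 20 to 20.9 − 15.0 = 5.9 points. Reversal is not inevitable: with a larger benefit (60% better, 30% same, 10% worse) and two independent symptoms, the table shows 1 − 0.9² = 19.0% worse and 0.6² = 36.0% better. The direction is right, but the net is 17 points instead of 50.

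**Reading B: each symptom has a severity at each visit, the highest is taken at each visit, and change is computed afterwards.** This was simulated with five severity levels, no true change, symptoms independent of each other, and a correlation between the two visits within each symptom. With three symptoms and a between-visit correlation of 0.5, 29.0% of boys were worse and 28.9% better; at 0.8, 22.4% and 22.5%. There is no systematic shift. What remains is loss of information: a boy whose worst symptom stays put while all the others improve is tabulated as unchanged.

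**The case against.** The strongest reply is that the lean towards worsening depends on Reading A, which the SAP does not state. The survey is also given at baseline, which fits a severity score differenced between visits, and under that reading the systematic shift disappears. This stands. The wording of SAP 5.8.9 and Protocol 7.19 favours a change rating but does not settle the matter.

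It also stands that every percentage above is illustrative. The aggregation clause is conditional on a category holding several symptoms, so some categories may hold one and be unaffected. Symptoms grouped together may also be strongly correlated, which weakens the effect.

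Three stronger inferences are tempting, and the documents do not support them:

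- *That the table will show deterioration where none exists.* This needs Reading A, more than one symptom per category, and correlation below one.
- *That boys or visits with more recorded symptoms will look worse.* Protocol 13.4.7 describes "individualized patient and parent/caregiver-reported changes in activities of daily living", and the SAP refers to the available symptoms. Neither says that the number rated differs between boys; the phrase may mean the non-missing items of a fixed list. The dependence on symptom count is real arithmetic under Reading A, but variation in the count is not shown.
- *That the SAP contradicts the protocol.* Protocol 10.5.6 asks only for a descriptive summary and sets no aggregation method, and a table of counts is descriptive. The SAP would prevail in any conflict: "Where conflicts exist between this SAP and the study protocols, the information contained in this SAP supersedes the protocol".

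Finally, this is a descriptive secondary endpoint in an open-label extension whose primary objective is safety. No test depends on the table, and under Reading A the error works against the drug. That limits the consequence, but it does not make a one-sided summary an accurate account of a two-sided endpoint. The SAP's use of highest severity for repeated adverse events is no parallel, because a safety table is meant to show the worst.

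**Conclusion.** The concern holds conditionally. Under either reading, the sole summary table of this endpoint represents a multi-symptom category by one symptom and cannot show improvement elsewhere in the category. Under the favoured change-rating reading it also leans systematically towards worsening: with three symptoms and no net change, by 48.8 − 0.8 = 48 points if symptoms are independent, 33.9 points at correlation 0.5 and 15 points at 0.9. Under the severity-then-difference reading that lean is absent. Which reading applies, and how large the effect would be, cannot be determined from the documents. The point is worth acting on because the correction is cheap and changes what the table can show; it does not touch the primary safety objective.

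**What to change.** In SAP 5.8.9:

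1. State what the score is (a change rating or a severity), its direction, and whether the maximum is taken before or after computing change from baseline.
2. For each category and visit, tabulate improved, unchanged and worsened by symptom; or give n (%) of boys with any symptom improved, any worsened, both, and neither. In either case report the number of symptoms rated.
3. Keep the worst-case row only if it is labelled as the worst symptom and shown beside this table.

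All of this uses data already collected. The cost is a few lines of SAP text and a slightly longer table.
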